## IV. Sample size considerations

The primary objective is to clarify the difference for the percent of weight loss (%) at 12 months after surgery between the simple nutrition counseling and the intensive nutrition counseling group. The percent of weight loss (%) in the simple nutrition counseling group would be about 10% with standard deviation of 5.407% [reference]. We expected that the intensive nutrition counseling group would reduce by 20% in simple nutrition counseling group, which would result in a percent of weight loss(%) of 8% in the intensive nutrition counseling group.

We calculated that 116 patients in each group would provide a power of 80% to determine the difference for percent of weight loss (%) in intensive nutrition counseling group compared to the simple nutrition counseling group (8% vs. 10%) with a standard deviation for both groups of 5.407%. The comparison will be made using a two-sided, two-sample equal-variance t-test, with a significance level of 0.05. After considering 10% loss to follow-up, we determined the total enrollment of 258 patients (129 in each group). An interim analysis was not planned.

[reference]: Ryu K, Bae J, Kim E, An JY, Choi M, Lee JH, et al. *Long-term effect of simplified dietary education on the nutritional status of patients after a gastrectomy*. *PLoS One* (2021) 16(5):E252168. doi: 10.1371/journal.pone.0252168

## **V. Data Analysis Plan**

The Full Analysis Set will be used for the primary efficacy analyses, and the Per-Protocol set will be used for supportive efficacy analyses.

The statistical methods of characteristics will be determined according to the type of variables. Continuous variables will be given as mean  $\pm$  standard deviation or median (interquartile range, IQR) and compared with a Student's t-test or Wilcoxon rank-sum test, depending on the normality of the distribution. For categorical variables, comparisons between groups will be summarized as frequency and percentile, and performed using a Chi-squared test or Fisher's exact test, as appropriate. To assess the association between two continuous variables, the correlation analysis will be performed and presented with scatter plots. In addition to, the standardized mean difference (SMD) will be calculated to estimate the difference for the mean values between two groups.

The primary objective of this study is to clarify the difference for the percent of weight loss (%) at 12 months after surgery between the simple nutrition counseling and the intensive nutrition counseling group. The difference for the percent of weight loss (%) at 12 months from baseline between two groups will be calculated, and the difference is tested using Student t-test. If the distribution for the percent of weight loss (%) violates the normality assumption, the non-parametric Wilcoxon rank-sum test will be used for sensitivity analysis. In addition, the percent of weight loss (%) at 1, 3, 6, 12 and 18 months will be analyzed using the generalized estimating equations (GEE) or mixed effects model to examine whether there is a difference between the two groups over time.

The repeated measures will be collected at baseline and each follow-up time points (1, 3, 6, 12, 18 months). All patients who had surgery and completed at least one baseline and

one follow-up (at any time point) measurement will be included. To estimate the difference between groups in change at each time points from baseline, the generalized estimating equations (GEE) or mixed effects model will be applied including time-by-group interaction term with the main effects. GEE method allows the inclusion of all participants, regardless of whether they have missing data at any follow-up time points, and will be adopted to take into account the within-patient correlation. The following effects will be estimated using GEE or mixed effects model:

- 1) differences in the percent of weight loss (%) between the two groups
- 2) whether the percent of weight loss (%) change over time within each group
- 3) whether there are differences in the percent of weight loss (%) changes over time between the two groups.

Missing data are expected due to drop outs and missed visits. Although substantial effort will be employed to minimize the missing data, it is inevitable that some missing data will occur. Various statistical analyses will be employed to perform statistical inferences that properly account for statistical uncertainty due to missingness. The percent of weight loss (%) is a subject-level variable and missing assessments would influence tests relative to treatment-by-time interactions. The primary analysis described above will be performed using all data. No patients will be deleted from the analysis because of partial data. To assess the sensitivity of results, weight loss will be analyzed using:

- 1) All patients regardless of missing data
- 2) Only patients who participated in all assessment visits and have no missing data
- 3) Rubin's multiple imputation

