### **2. Secondary objectives**

- 1) Nutritional parameters, Patient-Generated Subjective Global Assessment (PG-SGA)
- 2) Intake (kcal, protein) and eating habits (meal frequency/meal speed) assessed by 24-hour dietary recall.
- 3) Albumin (Unit: g/dL)
- 4) Hemoglobin (Unit: g/dL)
- 5) Iron panel [Total Iron-Binding Capacity (TIBC) (Unit:  $\mu$ g/dL), Ferritin (Unit: ng/mL)]
- 6) Absolute lymphocyte count (ALC) (Unit:  $10^3/\mu$ L)
- 7) Vitamin B12 (Unit: pg/mL)
- 8) Homocysteine (Unit:  $\mu$ mol/L)
- 9) Quality of life using the European Quality of Life questionnaire (EQ-5D)

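### The SAP assigns no clear analysis to the secondary blood markers, and neither rule that could apply adjusts for the patient's baseline value

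*SAP*

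**What the plan says.** Section I of the SAP states that the plan covers the methods for both the primary and the secondary outcomes. Section II.2, items 3 to 8, lists albumin, haemoglobin, TIBC, ferritin, absolute lymphocyte count, vitamin B12 and homocysteine among the secondary objectives.

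Section V mentions none of these markers. Two parts of it could apply to them:

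- **The general rule.** The second paragraph sets methods by type of variable. Continuous variables are "compared with a Student's t-test or Wilcoxon rank-sum test, depending on the normality of the distribution". The paragraph is introduced as dealing with characteristics. It gives no baseline term, transformation or time point.
- **The repeated-measures model.** A later paragraph begins "The repeated measures will be collected at baseline and each follow-up time points (1, 3, 6, 12, 18 months") and plans a GEE or mixed model for the group difference in change from baseline at each visit, with group, time and their interaction. That paragraph names no endpoint. The paragraph before it is about percent weight loss, and so are all three effects the model is to estimate, the first being "differences in the percent of weight loss (%) between the two groups".

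No baseline covariate and no log scale appear anywhere in the SAP.

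**The concern.** A reader cannot tell from section V which method produces the result for ferritin, vitamin B12 or any other marker, at which visit, or on which scale. Under the general rule, each patient's own baseline value goes unused, and the test depends on how the data look. The Wilcoxon branch also comes with no stated effect estimate or confidence interval. Under the repeated-measures rule, baseline enters only by subtraction. That is noisy when baseline and follow-up are weakly correlated, and noisier still for a right-skewed concentration on its raw scale.

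The markers are the trial's laboratory evidence on nutritional status. At stake are the precision of those comparisons and the freedom, after the data are seen, to choose among methods, scales and visits for seven markers.

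**Working it through.** **Inputs from the SAP (section IV).** A "two-sided, two-sample equal-variance t-test, with a significance level of 0.05"; 116 per group; 10% against 8% weight loss; SD 5.407%; 10% loss to follow-up.

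**The SAP's own figure.** The exact noncentral t calculation for a 2-point difference and SD 5.407 gives power 0.798 at 115 per group and 0.801 at 116, so 116 is reproduced. Then 116 / 0.9 = 128.9, so 129 per group and 258 in total. The SAP gives no corresponding figure for any blood marker.

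**Assumptions (not in the SAP).** The baseline-to-follow-up correlation ρ, and the spread and skewness of the markers. A range is shown for ρ.

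**Step 1: baseline adjustment on a scale where the data are normal.** Relative to an unadjusted comparison, the outcome variance is multiplied by 1 − ρ² for ANCOVA and by 2(1 − ρ) for a change score. Take an effect that gives the unadjusted test 80% power at 116 per group: (1.960 + 0.842) × √(2/116) = 0.368 SD.

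| ρ | Unadjusted | Change score | ANCOVA |
|---|---|---|---|
| 0.2 | 80% | 60% | 82% |
| 0.3 | 80% | 66% | 84% |
| 0.5 | 80% | 80% | 90% |
| 0.7 | 80% | 95% | 97.5% |

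ANCOVA is never worse than either alternative. The change score is worse than ignoring baseline when ρ is below 0.5.

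**Step 2: a skewed marker.** Assume a log-normal marker with log-SD 0.8 and true ratio 1.25. On the log scale the effect is ln 1.25 = 0.2231, and the unadjusted standard error is 0.8 × √(2/116) = 0.1050, so z = 2.124. Power is Φ(2.124 − 1.960) = 56.5%. With baseline adjustment, z is divided by √(1 − ρ²):

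- ρ = 0.2: z = 2.168, power 58%
- ρ = 0.3: z = 2.227, power 61%
- ρ = 0.5: z = 2.453, power 69%
- ρ = 0.7: z = 2.975, power 84%

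Simulation of the same setting for ρ from 0.2 to 0.7 gives 52 to 56% for Wilcoxon, 32 to 60% for a t-test on raw change (a single-visit stand-in for the change model), and 59 to 85% for log-scale ANCOVA. Type I error is about 5% throughout. The gains of log-scale ANCOVA are:

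- over Wilcoxon: about 4 points at ρ = 0.2 to 0.3 (runs varied up to about 6 at 0.3), and about 14 to 30 points at ρ = 0.5 to 0.7;
- over the t-test on raw change: about 24 to 28 points across the range.

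**Step 3: where the gain comes from.** The unadjusted log-scale test (56.5%) barely beats Wilcoxon (52 to 56%), because ranks do not change under a log transformation. A separate simulation with ρ = 0 and log-SD from 0.1 to 1.0 gave 77 to 79% for the normality-switched test and 79 to 81% for the log-scale model. The gain over Wilcoxon is therefore mostly baseline adjustment. Scale matters once a covariate model is used: at log-SD 0.8, raw-scale ANCOVA has 50% and 66% power at ρ = 0.5 and 0.7, against 67% and 85% on the log scale.

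**The case against.** The strongest reply is that the repeated-measures paragraph already covers the markers. Percent weight loss over time has been given its GEE or mixed model one paragraph earlier. The next paragraph starts afresh with repeated measures in general and, read as weight only, would largely repeat what precedes it. On that reading baseline is used. This is a fair reading and cannot be excluded. It does not settle the matter, because the listed effects name weight loss alone, and a change-from-baseline analysis still lacks the baseline covariate.

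A reader might infer that the SAP commits the markers to a raw-scale t-test that ignores baseline, and so loses much of the available power. The document does not support this. The t-test/Wilcoxon rule is introduced for characteristics and is not tied to the markers. Under marked skew it would select Wilcoxon, so raw t-test power is the wrong comparator. Nor does the SAP say that any marker is skewed, or that normality is judged visit by visit.

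It is also fair that an unadjusted comparison in a randomised trial is valid, that these outcomes are not powered, and that at correlations of 0.2 to 0.3 the gain over Wilcoxon is small. All of that stands. It limits the point to efficiency and clarity.

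**Conclusion.** The point holds as one of assignment and efficiency. Section V does not say how the markers in II.2 items 3 to 8 are analysed, although section I promises methods for secondary outcomes. Each rule that might apply leaves out the baseline value as a covariate. Neither rule is invalid.

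The power cost is conditional. Under the assumed log-normal marker it runs from about 4 points against Wilcoxon at correlations of 0.2 to 0.3 to about 14 to 30 points at 0.5 to 0.7, and is about 24 to 28 points against raw change. The correlation, log-SD and ratio are all assumptions, so no single figure can be claimed for any marker. The conclusion that baseline adjustment is at least as efficient does not depend on the value of the correlation. The change is worth making before analysis. It concerns secondary endpoints only; the primary endpoint and the sample size of 258 stand.

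**What to change.** In section V, state that each marker in II.2 items 3 to 8 is analysed by one repeated-measures model with group, visit, group-by-visit, the patient's baseline value and baseline-by-visit. Name the month-12 group contrast as the one of interest, reported with a 95% CI.

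Fix the scale per marker in advance. Use the log scale, reported as ratios of geometric means, for markers the study team expects to be right-skewed (for example ferritin, vitamin B12 and homocysteine), and the original scale for the others. Keep the t-test or Wilcoxon comparison as descriptive only.

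The cost is SAP wording. It needs no extra measurement, provided each marker is drawn at baseline as the repeated-measures paragraph implies. The one small drawback is that log-scale results are read as ratios rather than unit differences.

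### The primary t-test is valid but ignores baseline weight; naming it as a covariate in advance costs almost nothing and may give a small gain in precision

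*SAP*

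**What the plan says.** Section V of the SAP defines the primary comparison as the group difference in percent weight loss "at 12 months from baseline between two groups will be calculated, and the difference is tested using Student t-test". A Wilcoxon rank-sum test serves as a sensitivity analysis if normality fails. No covariate is named.

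The repeated-measures analysis is a GEE or mixed model "including time-by-group interaction term with the main effects"; no other term is listed. Entry to that analysis requires a baseline measurement: it begins "All patients who had surgery and completed at least one baseline" and goes on to require at least one follow-up value.

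Section IV sizes the trial on a "two-sided, two-sample equal-variance t-test, with a significance level of 0.05". The planned test and the sample-size test therefore agree.

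**The concern.** Percent weight loss has baseline weight as its denominator, so every patient who contributes an outcome also has this covariate. Adjusting for it would exclude nobody and need no new data.

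Dividing by baseline weight does not guarantee that percent loss is unrelated to starting weight. Heavier patients may lose a different percentage from lighter ones, and the SAP does not address this either way. If a relation remains, there are two consequences:

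- Variation that baseline weight could explain stays in the error term, and the confidence interval is wider than it need be.
- A chance difference in starting weight between the groups moves the treatment estimate. The t-test's interval allows for this on average over randomisations, but not given the imbalance that actually occurs.

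There is also a question of discipline. Section V provides for comparing characteristics between groups and for standardised mean differences, but does not say what follows if the groups differ. Naming the covariate now removes any later temptation to adjust because the baseline table looks uneven.

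**Working it through.** **Inputs from SAP section IV:** 116 evaluable patients per group (N = 232), SD 5.407 in both groups, difference 10 − 8 = 2 points, two-sided alpha 0.05, 10% loss to follow-up.

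**Assumed input:** r, the within-group correlation of baseline weight with 12-month percent loss. The SAP gives no value, so r = 0 to 0.4 is used as a range.

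**Step 1. Reproduce the plan.**
- SE = 5.407 × √(2/116) = 0.710, with 230 degrees of freedom.
- Noncentral-t power at 116 per group is 80.1%. At 115 it is 79.8%, so 116 is the smallest group size that reaches 80%.
- Allowing for loss: 116 / 0.90 = 128.9, so 129 per group and 258 in total. The plan's figures reproduce.
- Unadjusted 95% CI half-width: 1.970 × 0.710 = 1.40 points.

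**Step 2. Adjust for baseline weight.** The residual SD becomes 5.407 × √(1 − r²). One degree of freedom is lost (df = N − 3 = 229), and estimating the slope inflates the SE on average by √(1 + 1/(N − 4)) = √(1 + 1/228) = 1.0022. So

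SE = 5.407 × √(1 − r²) × √(2/116) × 1.0022.

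**Step 3. Imbalance.** If the groups differ in mean baseline weight by 1.96 standard errors, the unadjusted estimate shifts by r × 5.407 × 1.96 × √(2/116) = r × 1.392 points.

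| r | ANCOVA power at 116 per group | CI half-width | n per group for 80% power | Shift of the unadjusted estimate at a 1.96-SE imbalance |
|---|---|---|---|---|
| 0 | 79.9% | 1.40 | 117 | 0 |
| 0.1 | 80.3% | 1.39 | 116 | 0.14 |
| 0.2 | 81.5% | 1.37 | 112 | 0.28 |
| 0.3 | 83.5% | 1.34 | 106 | 0.42 |
| 0.4 | 86.3% | 1.28 | 98 | 0.56 |

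The unadjusted comparators are 80.1%, 1.40 and 116. Adjustment breaks even at r = 0.066. The largest loss is 80.1 − 79.9 = 0.2 points of power, at r = 0.

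**Step 4. Checks.** A simulation of 200,000 trials at each r, fitting the ANCOVA, gave power of 79.9, 80.4, 81.6, 83.4 and 86.4%. Charging only the lost degree of freedom, without the slope term, gives slightly higher values (80.1, 80.5, 81.7, 83.7 and 86.5%). The table is the more cautious of the two.

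**Step 5. Error rate given the imbalance.** Conditional on a 1.96-SE imbalance, the standardised unadjusted difference under no effect is approximately normal with mean 1.96r and variance 1 − r². Its chance of exceeding 1.96 in absolute value is about 6%, 8% and 10% at r = 0.2, 0.3 and 0.4, against a nominal 5%. Averaged over all randomisations it remains 5%.

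**The case against.** The strongest objection is that nothing here is wrong. A pre-specified unadjusted test that matches the sample-size basis is coherent, and preferring a more efficient estimator does not make it a defect. **This stands**, and it is why the point is offered only as an option.

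The benefit rests on a correlation that the documents do not supply. The outcome is already scaled to baseline weight, which should weaken that correlation, and at r = 0 adjustment is slightly harmful (117 per group instead of 116). **This also stands.** The payoff is nevertheless lopsided: at most 0.2 points of power lost, against gains of 1.4 to 6.2 points at r = 0.2 to 0.4.

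An imbalance of 1.96 SE is a tail case, reached or exceeded in about 1 trial in 20. At the median absolute imbalance (0.674 SE), the same formula gives shifts of only 0.05, 0.10, 0.14 and 0.19 points at r = 0.1 to 0.4. **This is correct**, and the larger shifts should be read as what could happen, not what is expected.

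Fixing no covariate in advance also guards against a later switch, since adjusting would be a visible departure from the SAP. **This is largely right for the primary test.** The argument from discipline is therefore secondary to the one from precision.

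The change has knock-on edits: the test sentence in section IV, and the Wilcoxon analysis, which is the rank counterpart of a two-sample test and not of ANCOVA. **Both are real but easily handled**, as set out in the fix. Finally, the longitudinal model's wording need not be an exhaustive list of terms. That is possible, but baseline weight is not named, so stating it would settle the question.

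**Conclusion.** The point holds as a low-cost, optional improvement. The planned Student t-test is valid, and the sample size is correctly derived from it. Pre-specified adjustment for baseline weight would be roughly neutral at r of 0.1 or less (power 79.9% to 80.3% against 80.1%). It would help modestly at r of 0.2 to 0.3 (81.5% to 83.5%) and more at 0.4 (86.3%). It would also remove the part of the estimate due to a chance imbalance in starting weight.

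These figures assume a linear relation with a common slope in both groups, the SAP's SD of 5.407 and difference of 2, and 116 evaluable patients per group. Because r is assumed, the size of the gain is uncertain; the bound on the loss is not sensitive to it. Adjustment does not resolve the exclusions after randomisation from the full analysis set, or missing 12-month weights. Those are separate matters.

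**What to change.** Before unblinding, amend section V of the SAP as follows:

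1. Make the primary analysis an ANCOVA of 12-month percent weight loss on group and baseline weight, reporting the adjusted difference with its 95% CI.
2. Add baseline weight as a covariate to the GEE or mixed model of percent weight loss.
3. Keep the unadjusted Student t-test as a supportive analysis, with the Wilcoxon rank-sum test attached to it.

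In section IV, keep the calculation and the enrolment of 258. Reword the test sentence to say that the size was derived from the unadjusted t-test and remains essentially adequate for the ANCOVA. If the protocol, which was not available here, names the primary test, its wording should be brought into line.

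The cost is two sentences in section V and one aligning edit in section IV. No new data or patients are needed. The statistical price is one degree of freedom, at most about 0.2 points of power if the correlation is zero.

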### **3. Definition of population for analysis**

#### **1) Full Analysis Set (FA set)**

We will evaluate the primary outcome “percent of weight loss (%) at 12 months after surgery between the simple nutrition counseling and the intensive nutrition counseling group” in the FAS population. In the FAS population, all randomized subjects are included, except following subjects.

- ① Subjects who do not meet the inclusion/exclusion criteria
- ② Subjects who have never received the nutrition counseling during the study period
- ③ Subjects who did not provide any data after baseline
- ④ Subjects diagnosed with other severe diseases affecting weight or receiving additional treatment (ex. Surgery, chemotherapy, etc.) after enrollment

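### The primary 12-month t-test cannot use patients without a 12-month weight, yet the SAP says its primary analysis uses all data and deletes nobody for partial data

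*SAP*

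**What the plan says.** - **Primary test.** In section V the 12-month difference from baseline is calculated and "the difference is tested using Student t-test". Section IV powers the same test: two-sided, equal variances, 5% level. Neither section ties an imputation method to it.
- **Analysis set.** Section V: "The Full Analysis Set will be used for the primary efficacy analyses". Section III.3 lists four exclusions from that set. The only one based on missing data is "Subjects who did not provide any data after baseline".
- **Longitudinal model.** It follows the t-test in section V as an extra: "In addition, the percent of weight loss (%) at 1, 3, 6, 12 and 18 months will be analyzed" by GEE or a mixed effects model. Of GEE the SAP says: "GEE method allows the inclusion of all participants, regardless of whether they have missing data at any follow-up time points".
- **Missing data.** At the end of section V, after a remark that "missing assessments would influence tests relative to treatment-by-time interactions", come the two sentences at issue: "The primary analysis described above will be performed using all data" and "No patients will be deleted from the analysis because of partial data". Rubin's multiple imputation appears only in the list of sensitivity analyses after them.

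**The concern.** A two-sample t-test of 12-month weight loss needs a 12-month value from every patient it includes. Without imputation it is an observed-case test. The two missing-data sentences claim the opposite for the primary analysis.

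The text can be read in two ways, and both leave a fault. If the primary analysis is the t-test, the test lacks the property claimed for it. If the sentences refer to the longitudinal model just before them, they are true of that model, but the label *primary* is on the wrong analysis and nothing says how a missing 12-month weight is handled in the powered test.

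The confirmatory p-value is at stake. One analyst could run the t-test on observed weights. Another, relying on the all-data statement, could report the model contrast or an imputed comparison. The results would differ, and the choice could be made after the data are seen.

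**Working it through.** **1. The SAP's own sample size.** Inputs from section IV: difference 10 − 8 = 2 points, SD 5.407 in both arms, two-sided alpha 0.05, 80% power, 10% loss.

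- The noncentral t calculation gives 115.7, rounded up to 116 per arm; power at 116 is 80.1%.
- 116 / (1 − 0.10) = 128.9, so 129 per arm and 258 in total. The SAP's figures reproduce.
- 129 − 116 = 13 per arm, or 26 of 258, are expected to have no 12-month outcome. The design therefore already assumes a test on about 116 observed values per arm.

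**2. One patient traced through the rules.** Take a patient weighed at baseline and at 1, 3 and 6 months, but not at 12.

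| Rule | Status of this patient |
|---|---|
| Full Analysis Set (III.3) | Included: has data after baseline |
| Student t-test at 12 months (V) | Not usable: no 12-month value |
| GEE or mixed model (V) | Included: baseline and at least one follow-up |
| All-data and no-deletion sentences (V) | Said to be kept in the primary analysis |

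Rows 2 and 4 conflict if the t-test is primary.

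**3. Precision at stake.** With 10% loss, n = 129 × 0.90 = 116.1 per arm, and SE = 5.407 × √(2/116.1) = 0.71.

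Let m = 0.10, let f be the share of missing patients who have an earlier weight (the rest leave the Full Analysis Set), and let ρ be the correlation of that weight with month 12. The SAP gives neither f nor ρ, so both are assumed.

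- n_FAS = 129 × [1 − m(1 − f)]
- q = m·f / [1 − m(1 − f)], the missing share within the Full Analysis Set
- effective n = n_FAS / [1 + (q/(1 − q))(1 − ρ²)]

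| f | ρ | Effective n per arm | SE | Power |
|---|---|---|---|---|
| observed cases only | – | 116.1 | 0.71 | 80.1% |
| 1 | 0.6 | 120.4 | 0.70 | 81.6% |
| 1 | 0.9 | 126.3 | 0.68 | 83.4% |
| 0.5 | 0.6 | 118.3 | 0.70 | 80.9% |
| 0.5 | 0.9 | 121.3 | 0.69 | 81.8% |

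**4. Bias of the observed-case test (hypothetical).** Assumptions: 10% missing at month 12, logistic dropout on month-6 weight loss, true difference 2.0, month-12 SD 5.407. The observed mean in an affected arm shifts by ρ × 5.407 × (mean standardised month-6 loss among those who stay), found by numerical integration. That mean is −0.039 at log-odds 0.4 per SD and −0.075 at 0.8.

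*Dropout related to weight loss in one arm, random in the other:*

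| Log-odds per SD | Month 6–12 correlation | Shift (points) | Shift / 0.71 | 95% CI coverage |
|---|---|---|---|---|
| 0.4 | 0.70 | 0.15 | 0.21 | 94.5% |
| 0.4 | 0.85 | 0.18 | 0.26 | 94.3% |
| 0.8 | 0.70 | 0.28 | 0.40 | 93.1% |
| 0.8 | 0.85 | 0.35 | 0.49 | 92.2% |

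*Same dropout rule in both arms* (month-6 SD 5, month-6 difference 0 to 2.0 points): the estimate lies between 2.00 and 1.97 at log-odds 0.4, and between 2.00 and 1.91 at 0.8. The largest shift is 0.09, and 0.09/0.71 = 0.13 standard errors.

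**The case against.** - **The t-test is plainly primary.** Sections IV and V name and power it and bring in the model only as an addition, so one loose sentence hardly displaces it. This has force, and it makes a wrong choice of analysis less likely. It does not make the sentence true of the t-test, nor does it supply a rule for a missing 12-month weight.
- **Partial data may mean an incomplete series of visits.** Sensitivity item 2 restricts the analysis to patients with every visit. Against that, the no-deletion sentence may say only that someone who missed month 3 stays in the primary analysis, which is true of an observed-case t-test. This is the best charitable reading. It still leaves the patient without a 12-month weight removed from the test, and it makes sensitivity item 1 a repeat of the primary analysis.
- **The loss is already paid for, and the stakes are small.** The inflation from 116 to 129 covers the lost power. Multiple imputation and the longitudinal model are both planned. The gain from partial data is about 0.8 to 3.3 power points, and the larger bias figures need a dropout pattern of which the SAP gives no sign. All of this stands and keeps the point well short of a fatal flaw.
- **Changing the primary method goes beyond the defect.** A wording correction would remove the contradiction. That is right, and it is offered below as the fallback. The method change is preferred because it makes the SAP's own no-deletion rule true for patients with follow-up weights, using methods already planned.

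**Conclusion.** The concern holds. As written, the all-data and no-deletion sentences are false of the powered primary test. If they are meant for the longitudinal model, they call the wrong analysis primary and leave missing 12-month weights in the primary test unaddressed. The point is partly one of wording, but it concerns the confirmatory result and should be fixed.

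At the SAP's 10% loss, about 13 patients per arm are affected. Using their earlier weights would raise power from 80.1% to at most 81.6–83.4%, assuming all have an earlier weight correlated 0.6–0.9 with month 12. Bias is negligible to small (at most 0.09 points) if dropout works the same way in both arms. It is 0.15–0.35 points if dropout depends on weight loss in one arm only, which is a hypothetical case. No figure in the SAP is wrong.

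**What to change.** Preferred: have the primary month-12 comparison use the partial data, and prespecify one of these two methods.

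1. The t-test on 12-month values multiply imputed separately by arm from the weights at the other visits, pooled by Rubin's rules.
2. The month-12 group contrast from a likelihood-based mixed model with group, visit as a categorical factor, and group-by-visit interaction.

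Keep the observed-case t-test as a sensitivity analysis.

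Fallback, if the observed-case t-test stays primary: state that it uses observed 12-month weights only, limit the all-data and no-deletion sentences to the longitudinal model, and keep multiple imputation as the sensitivity analysis.

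The cost is SAP wording and, for the preferred option, slightly more analysis work with data and methods already planned. No new patients, visits or measurements are needed, and the enrolment of 258 stays as it is.
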